- **Primary objective:** To determine the oral bioavailability and pharmacokinetics of compounds from a single administration of CAP in demented elderly humans receiving cholinesterase inhibitor treatment.
 - The primary endpoints for this study are the maximum concentration (C_{max}) and the area under the curve (AUC) of known compounds from *Centella asiatica* (triterpenes and caffeoylquinic acids and their metabolites) in human plasma.
 - Secondary endpoints are the time of maximum plasma concentration (t_{max}) and half-life ($t_{1/2}$) of the known bioactive compounds and their metabolites to help determine dosage intervals.
 - Another secondary endpoint will be temporal changes in ferric reducing ability of plasma (FRAP) as an indicator of antioxidant potential over time.
 - An additional endpoint will be the levels of triterpenes, caffeoylquinic acids, and their metabolites in a pooled urine sample collected over 10 h after CAP administration.

- **Secondary objectives:**
 - To assess the tolerability of acute administration of CAP in demented elderly humans. Additional secondary endpoints include tolerability and detection of acute adverse events through monitoring by participant interviews, biometrics, electrocardiography, laboratory assessment of liver and kidney function, vital signs and questionnaires.
 - To investigate the activation of the NRF2 antioxidant response element pathway in peripheral blood mononuclear cells (PBMC) over 6 hours following CAP administration.

Design and outcomes

This is an outpatient open-label phase 1 pilot clinical study using a blinded randomized crossover design of two doses (n=8) of a *Centella asiatica* water extract product (CAP). This study is to determine bioavailability, safety and acute tolerability of two doses of CAP in mildly cognitively impaired elders aged 65-85 on cholinesterase inhibitor therapy.

Outcomes:

- **Primary outcome:**
 - A change in pharmacokinetic parameters (C_{max} and AUC_{0-10}) of plasma analytes after treatment with a product made from a water extract of *Centella asiatica* (CAP) with a detectable difference between doses (2g and 4g).
- **Secondary outcomes:**
 - The time of maximum concentration (t_{max}) and half-life ($t_{1/2}$) of the known bioactive compounds and their metabolites to help determine dosage intervals
 - Temporal changes in ferric reducing ability of plasma (FRAP) as an indicator of antioxidant potential over time
 - Safety and tolerability of single doses of CAP determined by participant interviews, biometrics, electrocardiography, laboratory assessment of liver and kidney function, vital signs and questionnaires
 - The level of triterpenes, caffeoylquinic acids, and their metabolites in a pooled urine sample collected over 10 h after CAP administration.
 - Activation of the NRF2 antioxidant response element pathway in peripheral blood mononuclear cells (PBMC) over 6 hours following CAP administration.

Intervention and duration

This is a study using a product composed of a water extract of the botanical *Centella asiatica*. The C_{max} , T_{max} and other pharmacokinetic parameters and tolerability assessments of two doses of CAP (2g and 4g) will be compared to one another. Participants will be in the study for up to two months. The minimum time a participant could be on study would be six weeks.

Sample size and population

The target population is elders aged 65-85 years old with a diagnosis of mild cognitive impairment for which they are currently on cholinesterase inhibitor therapy. There will be 4 male and 4 female participants in the study. This is a randomized crossover study, so no stratification will be implemented in randomization.

1. STUDY OBJECTIVES

1.1. Purpose

The purpose of this study is to measure the oral bioavailability and pharmacokinetics of known bioactive compounds from a standardized *Centella asiatica* water extract product (CAP) in

mildly demented elders on cholinesterase inhibitor therapy. Compound levels will be measured in human plasma and urine over 10 hours after acute oral administration of two doses of the botanical extract product. The dose giving maximum plasma levels (C_{max}) closest to those observed in our mouse studies, the area under the curve (AUC_{0-10}), as well as the rate of clearance ($t_{1/2}$) of the known compounds and time of maximum concentration (t_{max}), will be identified. These data will be used to inform decisions on the dosage and dosing frequency for future clinical trials.

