1.4. Specific aims

Aim 1: To assess the bioavailability and rate of clearance of *Centella asiatica* derived compounds in mildly demented elders on cholinesterase inhibitor therapy through a pharmacokinetic study.

- **Hypothesis:** We hypothesize that the triterpene and caffeoylquinic acid components from *Centella asiatica* will be bioavailable, and a dose giving similar plasma levels to those associated with cognitive effects in mice can be achieved.

Aim 2: To determine the acute tolerability of a *Centella asiatica* product in mildly demented elders on cholinesterase inhibitor therapy.

- **Hypothesis:** We hypothesize that acute usage of the *Centella asiatica* product will be well tolerated and produce no severe adverse events.

Aim 3: To investigate whether activation of the NRF2 antioxidant pathway can be detected in PBMC of mildly demented elders on cholinesterase inhibitor therapy following ingestion of a *Centella asiatica* product.

- **Hypothesis:** We hypothesize that activation of the NRF2 pathway can be measured as increased NRF2 gene expression and/or nuclear protein levels in PBMC during a 6 hour period following ingestion of the *Centella asiatica* product.

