Human studies, although limited, support *Centella asiatica*'s ability to affect cognition and mood. Placebo-controlled trials showed that herbal extracts, or dried herb, improved cognitive function in healthy elderly³³ and middle-aged³⁴ volunteers. In elderly participants with mild cognitive impairment, investigators found improvements in cognitive test results (Mini Mental State Examination) following use of dried *Centella asiatica* for six months³⁵; however, no control group was incorporated. Unfortunately, these studies used highly variable *Centella* preparations that were poorly characterized and were either performed in cognitively normal individuals thereby limiting clinical applicability, or were not placebo-controlled. This warrants a robust, randomized, double blind, placebo-controlled study in cognitively impaired humans to examine the effects of a chemically well-characterized *Centella asiatica* extract on cognition.

[figure not shown]

Figure 1. *Centella asiatica* water extract improves learning and memory in aged female Tg2576 mice without altering β -amyloid accumulation. Tg2576 mice (20 month old) were exposed to *Centella asiatica* water extract (200mg/kg/day) in their drinking water for 2 weeks before and during testing (total 5 weeks). Left – Morris water maze escape times. Right – Soluble and insoluble fractions of A β were extracted from cortical tissue and analyzed via ELISA (bars represent means +/- standard error).

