Figure 2. Pharmacokinetic profile of monocaffeoylquinic acids, dicafeoylquinic acids and metabolites caffeic acid and ferulic acid in wild-type female mice. Six-month-old female mice (n=39) were administered *Centella asiatica* water extract (200 mg/kg) via oral gavage. Four mice were euthanized per time point and blood collected via cardiac puncture for analysis with HPLC-MS/MS.

Table 2. Pharmacokinetic parameters of caffeoylquinic acids and metabolites in mouse plasma after single oral administration of *Centella asiatica* water extract.

Analyte	C_{max} (ng/mL)	t_{max} (min)
Monocaffeoylquinic acids	84.3	15
Dicafeoylquinic acids	37.8	60
Caffeic acid	39.6	15
Ferulic acid	15.2	7.5
Isoferulic acid	2.5	7.5*
Dihydrocaffeic acid	13.1	240*

Dihydroferulic acid	Not detected	Not detected
Dihydroisoferulic acid	124	30*
4-methyl catechol	4.9	120*
4-ethyl catechol	0.94	90*
3-(3-hydroxyphenyl)propionic acid	84.5	7.5*

* Inconsistent time curve

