10.6. Specimen analysis

Each CAP derived analyte will be identified by its retention time and characteristic mass spectral fragmentation pattern using selected reaction monitoring. The peak area ratio to the appropriate internal standard will be identified and evaluated against the standard calibration curve of each analyte. Each analyte's concentration will be used to generate a concentration-time curve for pharmacokinetic profiling. Pharmacokinetic (PK) profiling of the triterpenes, CQAs and their metabolites will use non-compartmental analysis (NCA) to calculate common PK parameters such as peak concentration (C_{max}), the time at peak concentration (t_{max}) and the total 10 hour bioavailability represented by the total area under the curve (AUC_{0-10}). These will be compared to the mouse data in order to assess appropriateness of dosing level. Other calculable NCA metrics will also be determined, such as the elimination half-life ($t_{1/2}$) calculated from the profile tails and the mean residency time (MRT) of the compounds in plasma. Descriptive assessment will be done at each of the doses to give basic PK summarization of the various CA compounds and total antioxidant compounds measured by FRAP. NRF2 antioxidant pathway related gene and/or protein levels will be compared in PBMCs from the screening visit, the baseline study visit sample and hourly up to 6h following CAP administration. Dose dependence of the study outcomes will be determined by evaluation of the within-subject differences in study outcomes between the 2g and 4g CAP doses.

Assumptions of normality will be confirmed using outcome density distributions alongside utility from formal tests, such as the Anderson-Shapiro. In instances of normality violation, statistical transformation such as natural logs and square roots will be considered as will non-parametric equivalent tests such as the paired Wilcoxon rank-sum test. Standard diagnostics will be very conservative given the limited number of available subjects but clearly obvious outliers will be removed as necessary. Non-continuous variables such as t_{max} will have frequency distributions compared between doses using chi-square testing. Although all CA compounds of interest and PK parameters are defined a priori, multiple comparison correction to p-values will be applied as necessary, with final two-tail significance defined at $p < 0.05$.

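### A match to the mouse single-gavage Cmax cannot by itself show that plasma levels associated with cognitive benefit in mice were reached

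*Combined protocol and SAP*

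**What the plan says.** Section 1.1 states what will be identified: the dose whose Cmax is "closest to those observed in our mouse studies", together with AUC0-10, half-life and tmax. Of these, only Cmax carries a mouse-matching criterion. The same section says the data will inform dosage and dosing frequency in later trials.

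The Aim 1 hypothesis in section 1.4 gives the match its meaning: that "a dose giving similar plasma levels to those associated with cognitive effects in mice can be achieved".

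Section 10.6 lists Cmax, tmax and AUC0-10 and then says: "These will be compared to the mouse data in order to assess appropriateness of dosing level". It gives no mouse AUC, no tolerance and no rule for combining analytes.

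The mouse evidence is in two places. In section 2.2, Figure 1, aged Tg2576 mice with improved learning and memory received the extract "in their drinking water for 2 weeks before and during testing (total 5 weeks"), at 200 mg/kg/day. In section 3.1, Figure 2 and Table 2, plasma levels were measured in six-month-old wild-type mice given "water extract (200 mg/kg) via oral gavage". Section 3.1 also announces a further mouse bioavailability study with CAP, without stating its route or regimen.

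**The concern.** The reference level and the cognitive effect come from different animals under different regimens. One group received the daily amount as a single bolus and was sampled for plasma. The other drank the same nominal daily amount and was tested for cognition. No mouse in the documents has both a plasma level and a cognitive result.

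A bolus with an early peak normally produces a higher maximum than the same amount taken gradually. A human Cmax below the gavage Cmax could therefore be read as a failure to reach the relevant levels even if daily exposure was matched. A human Cmax equal to it could be read as success against a level the cognitively improved mice may never have had. Either reading would pass into the choice of dosage and dosing frequency that section 1.1 says these data will inform.

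**Working it through.** **The two sources side by side**

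| | Cognitive result (2.2, Figure 1) | Plasma levels (3.1, Figure 2 and Table 2) |
|---|---|---|
| Mice | Tg2576 females, 20 months | wild-type females, 6 months |
| Regimen | 200 mg/kg/day in drinking water, 5 weeks in total | 200 mg/kg, one gavage |
| Plasma level | not reported | Cmax and tmax only |
| Cognition | reported | not reported |

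Table 2 gives no AUC, no half-life and no triterpenes. Its values are measurements, so there is no figure of the plan to reproduce. Section 3.1 quotes a Cmax range of 15 to 2350 ng/mL while Table 2 runs from 0.94 to 124 ng/mL. That is a separate discrepancy, and nothing below depends on it.

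**Direction.** If the exposure from one gavage falls within 24 h, its peak cannot lie below its own 24 h mean. Under linear kinetics that mean equals the average level from the same daily dose taken over the day.

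**Size.** Assume one compartment, linear kinetics and first-order absorption with its rate set to reproduce tmax. Write D for the absorbed dose, V for volume and ke = ln 2 / half-life.

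- Gavage peak: Cmax = (D/V) × exp(−ke × tmax)
- Mean level over 24 h at the same daily dose: AUC/24 = D / (V × ke × 24)
- Ratio = 24 × ke × exp(−ke × tmax)

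Inputs: the four Table 2 analytes not marked as having an inconsistent time curve have tmax of 7.5 to 60 min (mono-CQAs 15, di-CQAs 60, caffeic acid 15, ferulic acid 7.5). Mouse half-life is not in the documents, so 0.5 to 4 h is an assumption.

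| Assumed half-life | tmax 7.5 min | tmax 15 min | tmax 60 min |
|---|---|---|---|
| 0.5 h | 28.0 | 23.5 | 8.3 |
| 1 h | 15.3 | 14.0 | 8.3 |
| 2 h | 8.0 | 7.6 | 5.9 |
| 4 h | 4.1 | 4.0 | 3.5 |

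Example, half-life 1 h and tmax 15 min: ke = 0.693 per h, and 24 × 0.693 × exp(−0.173) = 16.64 × 0.841 = 14.0.

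**Sensitivity**

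- If intake is spread over 12 h instead, the gavage peak is about 2 to 14 times the peak of that intake pattern over the same grid.
- Widening the half-life to 0.25 to 9.5 h gives 1.6 to 47 against the 24 h mean. The upper end comes from section 10.3, which expects 97% clearance in 48 h: 48 × ln 2 / ln(1/0.03) = 9.5 h. That is a prediction for participants, borrowed here only as a bound.
- Table 2 also has tmax of 90, 120 and 240 min, all marked inconsistent. At tmax 240 min and half-life 4 h the ratio is 4.16 × exp(−0.693) = 2.1. At half-life 1 h it is 16.64 × exp(−2.77) = 1.04. For still shorter half-lives the model needs absorption running well past 24 h, and the direction argument no longer applies. For late-peaking analytes the gap is small or undetermined.

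**The case against.** The strongest reply is that the mouse match carries little formal weight and already includes AUC. Section 10.6 compares AUC0-10 as well as Cmax with the mouse data. There is no tolerance or pass/fail rule. Aim 1 speaks of plasma levels rather than Cmax. The primary outcome (4.2, 10.5), the primary hypothesis (10.4) and the sample size (10.8) do not use the match. All of this stands, and it limits the point to the reading of Aim 1 and the use of the data for later dosing. It does not remove the point: section 1.1 still attaches its only matching criterion to Cmax, and section 1.4 still says what a match means.

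A reader might infer that AUC should simply replace Cmax as the deciding metric, because a gavage AUC equals the daily AUC from drinking water. The documents do not support that. Section 2.4 raises possible enzyme saturation for caffeoylquinic acids at higher doses, so a bolus AUC could exceed the AUC of the same amount taken slowly. The same section reports a human triterpene study in which 24 h AUC was much greater after seven days of treatment than after a single dose. It also describes second peaks and proposed enterohepatic recirculation, which make a one-compartment model doubtful. A gavage AUC would not remove the differences in strain, age and duration.

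A reader might also infer that any gavage Cmax is the wrong measure. That too goes beyond the text. No passage establishes whether peak or total exposure drives the effect, and section 2.4 itself reasons from a minimum neuroprotective concentration of 500 ng/mL in vitro. A gavage also resembles the participants' single dose more closely than drinking water does.

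**Conclusion.** The mouse Cmax in Table 2 is not shown to be the level present when cognition improved, so a Cmax match or mismatch alone cannot settle the Aim 1 hypothesis. It would go too far to say that the gavage Cmax is known not to be the effective level: no plasma level under the drinking-water regimen is reported, and drinking water is documented for Figure 1 only, since the regimens of the other cited cognition studies cannot be seen.

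For early-peaking analytes the excess over the 24 h mean is about 3.5 to 28 times, conditional on linear one-compartment kinetics, equal daily dose, even intake and a half-life of 0.5 to 4 h. For an analyte peaking at 240 min it is about 2 times at a half-life of 4 h. The size is therefore illustrative. For the early-peaking analytes the direction held at every half-life tried. The comparison of 2 g with 4 g and its power are untouched.

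**What to change.** 1. In section 1.1, bring the mouse comparison into line with section 10.6 by using AUC alongside Cmax. Compute mouse AUC from the existing time course for the analytes that have one, over a window matched to the human AUC0-10, or state the truncation.
2. In sections 1.1, 1.4 and 10.6, label the mouse reference as single-gavage exposure in wild-type mice. State that a Cmax match or mismatch alone will not be taken to show that levels associated with cognitive effects were, or were not, reached.
3. State that reading a gavage AUC as daily drinking-water exposure assumes linear kinetics and no difference between single and repeated dosing, that section 2.4 puts both in doubt, and that no mouse triterpene levels are shown.

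The cost is wording plus one AUC calculation per analyte with a usable mouse time course. The downside is that mouse AUC rests on about four animals per time point, and six of the ten analytes detected in Table 2 are marked as having inconsistent time curves. If the planned CAP mouse study sampled animals under the regimen of the cognition work, it would address the gap in route and duration directly. No dose is proposed.

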1.2. Primary goal

To determine the oral bioavailability and pharmacokinetics of known compounds from two single administrations of two different doses of a *Centella asiatica* product in mildly demented elders on cholinesterase inhibitor therapy.

1.3. Endpoints/objectives

- **Primary objective:** To determine the oral bioavailability and pharmacokinetics of compounds from a single administration of CAP in demented elderly humans receiving cholinesterase inhibitor treatment.
 - The primary endpoints for this study are the maximum concentration (C_{max}) and the area under the curve (AUC) of known compounds from *Centella asiatica* (triterpenes and caffeoylquinic acids and their metabolites) in human plasma.
 - Secondary endpoints are the time of maximum plasma concentration (t_{max}) and half-life ($t_{1/2}$) of the known bioactive compounds and their metabolites to help determine dosage intervals.
 - Another secondary endpoint will be temporal changes in ferric reducing ability of plasma (FRAP) as an indicator of antioxidant potential over time.
 - An additional endpoint will be the levels of triterpenes, caffeoylquinic acids, and their metabolites in a pooled urine sample collected over 10 h after CAP administration.
- **Secondary objectives:**
 - To assess the tolerability of acute administration of CAP in demented elderly humans. Additional secondary endpoints include tolerability and detection of acute adverse events through monitoring by participant interviews, biometrics, vital signs, electrocardiography, laboratory assessment of liver and kidney function, and questionnaires.
 - An exploratory end point will be the activation of the NRF2 antioxidant response element pathway in peripheral blood mononuclear cells (PBMC) over 6 hours following CAP administration.

1.4. Specific aims

Aim 1: To assess the bioavailability and rate of clearance of *Centella asiatica* derived compounds in mildly demented elders on cholinesterase inhibitor therapy through a pharmacokinetic study.

- **Hypothesis:** We hypothesize that the triterpene and caffeoylquinic acid components from *Centella asiatica* will be bioavailable, and a dose giving similar plasma levels to those associated with cognitive effects in mice can be achieved.

Aim 2: To determine the acute tolerability of a *Centella asiatica* product in mildly demented elders on cholinesterase inhibitor therapy.

- **Hypothesis:** We hypothesize that acute usage of the *Centella asiatica* product will be well tolerated and produce no severe adverse events.

Aim 3: To investigate whether activation of the NRF2 antioxidant pathway can be detected in PBMC of mildly demented elders on cholinesterase inhibitor therapy following ingestion of a *Centella asiatica* product.

- **Hypothesis:** We hypothesize that activation of the NRF2 pathway can be measured as increased NRF2 gene expression and/or nuclear protein levels in PBMC during a 6 hour period following ingestion of the *Centella asiatica* product.

2. BACKGROUND

2.1. Alzheimer's Disease

Alzheimer's disease is a severe form of cognitive impairment and one of the most expensive and debilitating conditions known to modern medicine. The National Institute of Aging suggests that greater than five million Americans may have Alzheimer's disease, making it the sixth leading cause of death in the United States.¹ In 2016 alone, government health agencies (Medicare and Medicaid) spent an estimated \$160 billion on Alzheimer's disease with a projected 365% increase by 2050.²

The pathogenesis of Alzheimer's disease is highly complex. Current evidence suggests it is a combination of genetics, environment and lifestyle factors making the development of treatments very challenging. Its most striking pathological feature is the accumulation of β -amyloid (A β) plaques within the brain.³ Current pharmaceutical investigation is aimed at preventing the accumulation of, or promoting the clearance of these neurotoxic plaques (anti-amyloid immunotherapy)^{4,5}; however, recent trials of such agents have failed to produce a significant clinical effect on Alzheimer's disease.^{6,7} Drugs currently FDA-approved for the symptomatic treatment of Alzheimer's disease are either cholinesterase inhibitors⁸ or act at the N-methyl-D-aspartate (NMDA) receptor.^{9,10} Unfortunately, these treatments do not influence disease progression, and their effectiveness is highly variable.

Beyond cognitive impairment, Alzheimer's disease also has significant comorbidities including insomnia, depression¹¹ and anxiety.¹² Multiple interventions are often needed to manage these symptoms affecting patient compliance and safety. This warrants further investigation into effective, inexpensive and well-tolerated treatments for Alzheimer's disease and its comorbidities.

Gender differences have been observed in the incidence, development and progression of Alzheimer's disease, and in response to interventions targeting cognitive impairment. Women develop cognitive disability more rapidly compared to men.^{13,14} Previous studies of intranasal insulin for cognition showed functional abilities were better preserved in women compared to men.¹⁵ These differences highlight the importance of evaluating responses to any agent in both males and females. As part of this proposed project we will evaluate potential gender differences in bioavailability and pharmacokinetics.

2.2. *Centella asiatica*

Centella asiatica is a highly regarded botanical reputed in Eastern medicine to increase intelligence and memory.¹⁶ In Western countries, it is sold as the dietary supplement "gotu kola"¹⁷ for use in improving brain health and cognitive function. Preclinical studies have shown that *Centella asiatica* extracts have biological effects of relevance to memory, learning, aging, mood and potentially disease progression in Alzheimer's disease.¹⁸ Water extracts of *Centella asiatica* have improved learning and memory in wild-type rats,¹⁹ wild-type mice,^{20,21} and rats subjected to central nervous system toxicity.^{22,23} In addition, similar extracts have been shown to modify the brain structure by increasing hippocampal neuron dendritic arborization in adult

rats,²⁴ neonatal rats,²⁵ and neonatal mice,²¹ potentially contributing to the observed cognitive changes. With regards to mood and behavior, ethanol extracts given to mice subjected to chronic and acute stress²⁶ and sleep deprivation²⁷ demonstrated anxiolytic properties. Similar ethanol extracts revealed antidepressant properties in rats.²⁸

With applications specific to Alzheimer's disease, one study showed that long-term usage of a *Centella asiatica* extract (six months) reduced β -amyloid plaque burden in a mouse model of Alzheimer's disease²⁹; however, studies performed at Oregon Health and Science University (OHSU) suggest that water extracts of *Centella asiatica* may achieve its cognitive effects without a direct action on β -amyloid (Figure 1).³⁰ Rather, *Centella asiatica* appears to affect downstream targets protecting neurons from β -amyloid induced neurotoxicity.^{20,31,32} This suggests that *Centella asiatica* may be able to limit disease progression even when β -amyloid deposition has already taken place, thereby representing a novel treatment mechanism, potentially complementary to the medications in development.

Human studies, although limited, support *Centella asiatica*'s ability to affect cognition and mood. Placebo-controlled trials showed that herbal extracts, or dried herb, improved cognitive function in healthy elderly³³ and middle-aged³⁴ volunteers. In elderly participants with mild cognitive impairment, investigators found improvements in cognitive test results (Mini Mental State Examination) following use of dried *Centella asiatica* for six months³⁵; however, no control group was incorporated. Unfortunately, these studies used highly variable *Centella* preparations that were poorly characterized and were either performed in cognitively normal individuals thereby limiting clinical applicability, or were not placebo-controlled. This warrants a robust, randomized, double blind, placebo-controlled study in cognitively impaired humans to examine the effects of a chemically well-characterized *Centella asiatica* extract on cognition.

[figure not shown]

Figure 1. *Centella asiatica* water extract improves learning and memory in aged female Tg2576 mice without altering β -amyloid accumulation. Tg2576 mice (20 month old) were exposed to *Centella asiatica* water extract (200mg/kg/day) in their drinking water for 2 weeks before and during testing (total 5 weeks). Left – Morris water maze escape times. Right – Soluble and insoluble fractions of A β were extracted from cortical tissue and analyzed via ELISA (bars represent means +/- standard error).

